6.1.20 End of Study

The end of study is defined as the date on which all patients have their last visit or 1 year after the last patient has their first visit, whichever comes first.

6.2 Discontinuation or Withdrawal

6.2.1 Discontinuation of Treatment

6.2.1.1 Permanent Discontinuation of Treatment

The investigator has the right to discontinue a patient from the study for any medical condition that the investigator or sponsor determines is in the best interest of the patient; reasons may include non-compliance (eg, missed doses, visits) or pregnancy.

Any patient who discontinues treatment should be encouraged to return to the study site for an EOT Visit and continue with the remaining study visits. The primary reason(s) for discontinuation must be recorded on appropriate CRF.

Patients must be discontinued from treatment for disease progression, withdrawal of consent, intolerable toxicity, as outlined in [Table 8](#), [Table 9](#), and [Table 10](#), repeated non-compliance or poor compliance, commencement of other antitumor treatment during the study, pregnancy, loss to follow-up, termination of the study by the sponsor, death, or end of the study.

Patients may receive a maximum of 6 cycles of therapy unless the following are met:

- Patients with AML must have a partial response (PR) or better based on the 2017 ELN criteria ([Appendix 8](#)).
- Patients with HR-MDS must have a hematological response or better based on the IWG Criteria ([Appendix 12](#))
- Patients with AITL must have a stable disease (SD) or better based on the Lugano Classification ([Appendix 9](#)).

6.2.1.2 Temporary Treatment Discontinuation

Patients who achieved adequate response after HMPL-306 treatment and meet other criteria for HSCT treatment can undergo HSCT after discontinuing HMPL-306 treatment, but they will continue to be retained in the study to perform efficacy follow-up and subsequent treatment recorded (Section [6.1.19](#)). If the patient discontinues HMPL-306 treatment for HSCT treatment but eventually fails to receive HSCT treatment, HMPL-306 therapy can resume after sponsor approval; if the patient fails HSCT treatment and has recurrent hematological malignancy with mIDH and then HMPL-306 treatment can resume after request from the investigator and sponsor approval.

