4.1.1 Part 1 (Dose Escalation)

The first part of the study is dose escalation, where cohorts of patients will receive ascending oral doses of HMPL-306 to determine MTD and/or the recommended phase 2 dose (RP2D). The modified toxicity probability interval-2 (mTPI-2) ([Greenberg 2012](#), [Guo 2017](#)) design will be used to perform dose escalation and MTD/RP2D determination. Briefly, the mTPI-2 method uses a Bayesian framework and a hierarchical model to compute the dose escalation based on the interval between the toxicity rate of each dose level and target probability ([Greenberg 2012](#), [Guo 2017](#)). This study is designed targeting a dose-limiting toxicity (DLT) rate of 20% with an equivalence interval of 15% to 25%.

Like the 3+3 design, the mTPI-2 method incorporates prespecified escalation rules that can be presented in a table ([Table 5](#)). As shown in [Table 5](#), the number of patients dosed at a given dose level are shown in the columns, while the rows indicate the number of DLTs experienced. The escalation/de-escalation rules from the table will be used for each dose level evaluated; the patient numbers and DLTs do not carry over from cohort to cohort. As an example, within a cohort:

- If none of the 3 patients experience a DLT → escalate the dose (“E” at column 3 row 0) to the next dose level cohort.
- If 1 out of 3 patients experience a DLT → de-escalate to a lower dose level (“D” at column 3 row 1).
- If 2 out of 3 patients experience a DLT → the dose is determined to be unacceptably toxic and will not be used again, de-escalate to a lower dose level (“DU” at column 3 row 2).
- If 1 out of 5 patients experience a DLT → stay at the same dose level (“S” at column 5 row 1).

The following rules apply during dose escalation:

- Starting dose at Cohort 1 is **100** mg.
- Although in the mTPI-2 method the cohort size is not fixed, at least 3 patients will be enrolled at each dose level. When all patients at a dose level complete DLT assessment, the study will escalate to the next dose level and another minimum of 3 patients will be recruited in this order until RP2D or MTD ([Table 5](#)).
- The sample size of a dose cohort that has already passed the preliminary DLT assessment (3 to 6 patients) and shown efficacy (eg, to include other efficacy signal for each tumor type) can be extended to 12 patients in order to further evaluate the safety and efficacy signals of that particular dose.

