DLT is defined as occurrence of any treatment-emergent adverse event (TEAE) as described in Section 8.1.3 during the DLT assessment window, unless clearly unrelated to the study drug as per investigator's discretion.

DLT Assessment Window:

For all patients in dose escalation, DLTs will be assessed during the DLT assessment window. This is the first 28 days of continuous study treatment (C1D1 through C1D28), and does not include the dose administered during PK week.

DLT-Evaluable Patient:

A patient is DLT-evaluable if the following criteria are met:

- has received at least 75% of the assigned dose of study drug during the DLT assessment window

OR

- has not completed DLT assessment period due to a DLT

For decisions on dose escalation, each dose cohort shall present the protocol-required numbers of DLT-evaluable patients. Patients who are not DLT-evaluable in a dose cohort may be replaced to guarantee the protocol-required number of DLT-evaluable patients for dose escalation evaluations.

Patients who complete the DLT assessment window will be allowed to continue treatment until disease progression, intolerable toxicity, withdrawal of consent, lost to follow-up, end of study, conditions are met per Section 6.2.1, or death, whichever comes first.

Maximum Tolerated Dose

The MTD determination will be driven by the mTPI-2 method. The MTD will be any doses with true toxicity probability in the equivalence interval. For this study, the equivalence interval is defined as 15% to 25%.

Recommended Dose of the Expansion Cohort and Phase 2 Clinical Study (RP2D)

RP2D determination will take the following criteria under consideration:

- Determination of MTD achieved during the dose escalation part
- Assessment of safety, PK, and PD

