6.1.4 Prior and Concomitant Medications and Concomitant Procedures

Concomitant medications may include any prescription or over-the-counter (OTC) medications used by a patient. During the Screening Period, all medications taken by a patient within 28 days prior to HMPL-306 administration should be recorded in a case report form (CRF). At scheduled subsequent visits, any drugs taken during that period and within 30 days after end of treatment should be recorded in the CRF. Subsequent new transplantation pretreatment regimens and new antitumor treatment regimens, including HSCT, during the Safety and Efficacy Follow-up Periods will also be recorded. Prior and concomitant therapies are discussed in detail in Section [7.4.1](#) and Section [7.4.2](#).

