6.1.13 Safety Evaluation

AEs emerging as a result of protocol-required procedure(s) are collected, even during pre-screening period if applicable. AEs are collected from the signing of the ICF until 30 days after the end of treatment or initiation of new antitumor therapy. Related AEs will be followed

until they are recovered to the baseline status, already in a stable state as assessed by the investigator, start of new antitumor therapy, lost to follow-up, death, withdrawal of informed consent, end of study, or it has been confirmed the AEs are unrelated to the study drug.

Serious adverse events (SAEs) are collected from the signing of the ICF (pre-screening ICF if applicable) until 30 days after the end of treatment or initiation of new antitumor therapy, whichever is earlier. After this 30-day period, and if the patient has not started any other antitumor treatment, investigators should report only SAEs considered to be related to the study drug.

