6.1.19 Follow-up Period

Safety Follow-up

All patients who have completed an EOT Visit will have a Safety Follow-up Visit. The Safety Follow-up Visit will be conducted at 30 days (± 7 days) from EOT Visit.

AEs related to the study drug will be followed until resolution and SAEs will be followed until resolution regardless of the relationship to the study drug.

All female patients of childbearing potential must complete a pregnancy test (serum or urine) during the Safety Follow-up Visit. Pregnancy testing should be repeated for patients with suspected pregnancy. This is not applicable for postmenopausal female patients (defined as at least 12 months of amenorrhea without alternative medical cause), and the date of menopause should be recorded instead.

Efficacy Follow-up

Patients who discontinue the study drug due to reasons other than disease progression, death, lost to follow-up, or withdrawal of consent will remain on study for tumor assessments and will be followed every 12 weeks (± 14 days) from the EOT visit or last assessment, until disease progression, initiation of new anticancer therapy, withdrawal of consent, lost to follow-up, death, conditions are met per Section [6.2.1](#), or the end of the study, whichever comes first.

Survival Follow-up

All patients will be followed for survival status every 12 weeks (± 14 days), until death, lost to follow-up, or withdrawal of consent. Survival information can be obtained via phone and information will be documented in the source documents and relevant CRFs.

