8.2 Adverse Event Reporting

8.2.1 Adverse Event Reporting Period

After informed consent, but prior to initiation of study drug, all AEs and SAEs regardless of attribution will be collected. After initiation of study drug, all SAEs and AEs regardless of attribution will be collected until 30 days after the end of treatment or start of a new antitumor therapy, whichever is earlier. After this 30-day period, and if the patient has not started any other antitumor treatment, then investigators should report only SAEs that are considered to be related to the study drug until study discontinuation.

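### When HMPL-306 is resumed after a failed transplant, no rule reopens adverse event collection or the SAP on-treatment windows, yet the resumed days count as exposure

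*Protocol*

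**What the plan says.** - **Resumption.** Protocol 6.2.1.2 allows responders to stop HMPL-306 for HSCT while staying in the study. Dosing may restart if the transplant fails and the patient "has recurrent hematological malignancy with mIDH and then HMPL-306 treatment can resume after request from the investigator and sponsor approval". No safety-collection or analysis rule is attached.
- **Collection.** Under protocol 8.2.1, AEs and SAEs after the first dose "will be collected until 30 days after the end of treatment or start of a new antitumor therapy, whichever is earlier". It continues: "After this 30-day period, and if the patient has not started any other antitumor treatment, then investigators should report only SAEs" judged related to study drug. Section 6.1.13 is similar ("AEs are collected from the signing of the ICF until 30 days after the end of treatment or initiation of new antitumor therapy"), although there the earlier-of-the-two qualifier is attached only to the SAE sentence.
- **Class of HSCT.** Protocol 6.1.4 speaks of "new antitumor treatment regimens, including HSCT" and names transplant pretreatment regimens beside them. SAP 5.2.6 has a stem cell transplant item under subsequent procedures. SAP 5.2.6.3 defines subsequent procedures as those after study drug was discontinued, without separating temporary from final discontinuation.
- **SAP windows.** The treatment period (4.1.4), the TEAE rule (4.4.2) and on-treatment death (5.2.11.3) all end at the earlier of 30 days after the last dose (plus 7 for by-visit parameters) and the start of subsequent anti-tumor therapy. Section 4.4.2(ii) still counts treatment-related SAEs after that.
- **Exposure.** SAP 4.1.1 and 4.3 run exposure to the last non-zero dose.
- **Protocol TEAE definition.** Protocol 9.2.4 ends TEAEs at 30 days after end of treatment and has no cut at subsequent therapy.

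**The concern.** Safety is the primary objective of both parts, and the SAP shows safety by dose level. For a patient who takes this route, the exposure table includes the second course of drug, but most of the safety findings from that course are excluded from the tables read beside it. The numerator and denominator then cover different days. The time lost is time on study drug, in a heavily treated patient whose tolerance after transplant would be of real interest. A death while taking HMPL-306 would be tabulated as a follow-up death.

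**Working it through.** The documents give no figure to reproduce. The check sets the rules side by side and then applies them to assumed dates.

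**1. Does HSCT close the windows?** Yes, on the literal text. Protocol 6.1.4 and SAP 5.2.6 and 5.2.6.3 make an HSCT after stopping HMPL-306 a new or subsequent therapy. If conditioning starts first and is recorded as anti-tumor treatment, it closes them sooner.

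**2. Does anything reopen them?** No such rule appears in protocol 6.1.13, 6.2.1.2 or 8.2.1, or in SAP 4.1.4, 4.4.2 or 5.2.11.3.

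**3. Where do findings from resumed days go?**

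| Finding | Result |
|---|---|
| Dosing days | Counted as exposure |
| Non-serious AEs | Not TEAEs; listed if recorded |
| Unrelated SAEs | Not TEAEs; listed if recorded |
| Related SAEs (missing causality counts as related) | TEAEs under 4.4.2(ii), if recorded; 8.2.1 asks for them only if no other antitumor treatment has started |
| Laboratory, ECG and vital signs by visit | Outside the summaries; listed |
| Deaths | In the overall death count, but classed as follow-up deaths |

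**4. Illustration.** All dates are assumed: daily dosing on days 1 to 112, HSCT on day 140 with a complete date, resumed dosing on days 300 to 383.

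- Resumed days: 383 − 300 + 1 = 84.
- Protocol collection closes at min(112 + 30, 140) = day 140.
- SAP window ends at min(383 + 30, 140 − 1) = day 139. Conditioning c days before HSCT moves this to 139 − c.
- Resumed days outside the window: 84 of 84.
- Days on drug: 112 + 84 = 196, so 84/196 = 43% of dosing days lie outside.
- A death on day 350, 383 or 400 is a follow-up death.

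Varying only the length of resumed treatment, 1 to 6 cycles of 28 days puts 28 to 168 on-drug days outside. The illustration has 4 + 3 = 7 cycles. Protocol 6.2.1.1 caps treatment at 6 cycles without PR or better, and does not say how that applies after relapse. If the cap held, 2 resumed cycles (56 days) would be possible, all outside.

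**5. The other reading, for comparison.** If the HSCT were not subsequent therapy, the window would run to 383 + 30 = day 413. No resumed day would be lost, but off-drug days 143 to 299 (157 days), including post-transplant time, would count as on-treatment.

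**6. Partial dates (secondary).** SAP 5.1.2.7 moves an imputed therapy date that falls before the final dose to the day after it. Here that is day 384, so the window ends on day 383. Inclusion of the resumed days then depends on whether the HSCT date is complete.

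**7. SAP against protocol.** Under protocol 9.2.4, AEs on resumed drug are TEAEs. The SAP rule is narrower, and SAP section 7 does not list this among its changes.

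**The case against.** **The classification may look open.** Protocol 6.1.19 runs efficacy follow-up "until disease progression, initiation of new anticancer therapy, withdrawal of consent, lost to follow-up, death", while 6.2.1.2 keeps HSCT patients in it, and SAP 5.1.2.7 presumes that subsequent therapy follows the last dose. A reader might infer that the documents leave the status of the HSCT undecided. They do not support that. The retention in 6.2.1.2 is a stated exception to a general rule, 5.1.2.7 is a date-imputation rule, and three other places class the HSCT as new or subsequent. If it were not subsequent, no resumed day would drop out.

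**AEs would be collected anyway.** Protocol 8.4 has investigators ask about AEs at every contact and record them, the Schedules of Events collect AEs at treatment visits, and 7.5.2 requires dose changes for related AEs. This stands in part: sites would probably record many events. But 8.2.1 is the section that fixes the reporting period, and its stop is explicit. Recording also does not bring an event into the SAP tables.

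**Stopping at subsequent therapy is a sound convention.** It keeps transplant toxicity out of the drug's safety profile. That is right for the transplant interval, but not for later days on study drug.

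**The partial-date case is remote.** This is accepted. Transplant dates are rarely incomplete, and 5.1.2.7 first asks for every effort to establish the sequence.

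**Conclusion.** The gap is real and minor. Read literally, the rules count resumed dosing as exposure while leaving non-serious AEs, unrelated SAEs and by-visit safety data from those days out of the summaries, and they class deaths on resumed drug as follow-up deaths. The SAP also narrows the protocol's TEAE definition without saying so.

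The number affected is unknown and may be zero. The route needs response, HSCT, recurrence with mIDH, an investigator request and sponsor approval. The day counts rest on assumed dates.

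Three stronger readings are not supported:

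- Because "at least 3 patients will be enrolled at each dose level" (extendable to 12), a reader might infer that one such case removes 1 of 3 to 1 of 12 patients from a cohort's safety data. It does not. The patient stays in the safety set with every event from the first period, and only new or worse events after HSCT are at issue.
- Deaths are not lost. SAP 5.2.11.3 counts all of them, and only the on-treatment label changes.
- Dose finding is not affected. DLTs are assessed in cycle 1, days 1 to 28.

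**What to change.** - **Protocol 8.2.1 and 6.1.13:** add that if HMPL-306 is resumed under 6.2.1.2, full AE and SAE collection restarts at the first resumed dose and continues to 30 days after the final dose.
- **SAP 4.1.4, 4.4.2 and 5.2.11.3:** define a second on-treatment period from the first resumed dose to 30 days (plus 7 for by-visit parameters) after the final dose, shown separately from the first.
- **SAP section 7:** list the cut at subsequent therapy as a change from protocol 9.2.4.
- **SAP 5.1.2.7 (secondary):** for patients who resume, compare a partial HSCT or conditioning date with the last dose before HSCT.
- **Efficacy censoring:** unchanged.

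In the illustration the periods become days 1 to 139 and 300 to 413 (420 for by-visit data). All 84 resumed days are then inside, days 140 to 299 are outside, and deaths on days 350, 383 and 400 are on-treatment.

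The cost is one sentence in each of two protocol sections, a little programming and one more display. If the protocol can no longer be amended, the SAP changes can still be made before database lock for data already recorded. If no patient resumed, the SAP text costs nothing further.

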6.2.1.3 Withdrawal from Study

All study patients have the right to voluntarily withdraw from study at any time. During the period of treatment and follow-up, a patient who withdraws consent to continue participation in the study will not be followed for any reason after consent has been withdrawn. Every effort should be made to obtain information on patients who discontinue the study drug but who do not withdraw consent to continue participation in the study. If a patient withdraws consent for disclosure of future information, the sponsor may retain and continue to use any data collected before such a withdrawal of consent.

If a patient withdraws from the study, such a patient may request destruction of any samples taken and not tested. The investigator must also document requested destruction in the site study records.

6.2.1.4 Replacement of Patients

Patients who are not DLT-evaluable in a dose cohort may be replaced to guarantee the protocol-required number of DLT-evaluable patients for dose escalation evaluations. Patients who are not eligible for response assessment (defined as those patients who completed a follow-up tumor assessment after cycle 2) in Part 2 of the study may be replaced.

6.2.1.5 Patients Lost to Follow-up

A patient will be considered lost to follow-up if the patient repeatedly fails to return for scheduled visits and is unable to be contacted by the study site.

Before a patient is deemed lost to follow-up, the investigator or designee must make every effort to regain contact with such patient (where possible, 3 telephone calls and, if necessary, a certified letter to patient's last known mailing address or local equivalent methods). These contact attempts should be documented in that patient's medical record. Should a patient continue to be unreachable, such patient will be considered withdrawn from the study.

6.2.2 Study Stopping Rules

Safety will be monitored continuously throughout the conduct of the study by a standing SRC. There will be periodic review of emerging data on safety, PK, drug exposure, TE, PD, and clinical response to determine continuation (or otherwise) of individual patient, cohorts, arms, or entire dose expansion part. If the study is halted as per Study Stopping Rules (Section 6.2.2.2) in either the dose escalation part or the dose expansion part, the study will only be restarted after Regulatory Approval as per local regulations.

Dose stopping rules for individual patients common to both dose escalation and dose expansion parts include:

1. DLTs that occur outside the DLT assessment window (DLT-equivalent) that have not resolved to Grade 1 or lower within 14 days, or after medical intervention as specified in Section 4.1.1.
2. Progression of disease that leads to treatment discontinuation
3. In the opinion and recommendation of the PI, or individual patient on their own, may withdraw from study at any time
4. If there is documented evidence of repeated non-compliance

6.2.2.1 Stopping Rules for Individual Patient

Dose Escalation:

Dosing will stop for an individual patient if:

DLT has not returned to Grade 1 or lower within 14 days

See Section 4.1.1 for details on dose escalation Part 1, DLT, and safety assessment.

Dose Expansion:

1. DLT-equivalent event has not resolved (even with medical intervention) within 14 days, or has re-occurred again at a de-escalated dose level
2. Resolution in severity (down-grade) and/or duration (within 14 days) of DLT-equivalent event will determine dose interruption, reduction, or discontinuation for the individual
3. Resolution of DLT-equivalent event will determine if the patient will resume treatment, at the discretion of investigator, at:
 - the same dose level
 - a lower dose
 - discontinue treatment altogether

6.2.2.2 Stopping Rules for a Cohort or the Study

Dose Escalation Part

The stopping rules at a cohort level are based on mTPI-2 method and defined in [Table 5](#). There will be no escalation to the next higher dose level cohort, until all available data from the current dose level cohort have been reviewed by SRC, who will then recommend appropriate dose escalation, de-escalation, or discontinuation.

This dose escalation part will be suspended, interrupted, or discontinued before MTD is attained based on:

1. Recommendation of SRC, and/or
2. Results of the analysis of emerging PK data suggesting that drug exposure or TE is saturated.

[figure not shown]
The dose escalation part of the study will prematurely end when any of the following conditions are met:

1. Excessive toxicity is present in the initial dose, ie, if DLT is observed in 1 out of 3 patients at the first dose level. If this occurs at the initial dose level, data will be reviewed by the SRC to determine next steps for the study.
2. Although no excessive toxicity is present in the first dose level cohort, if the dose returns to the initial dose according to the rules in [Table 5](#) and excessive toxicity is present at the initial dose (for example, 2 or more patients with a DLT are observed in 6 patients).

Dose Expansion Part:

This part utilizes MTD or RP2D that has been determined as safe by SRC based on the conclusion of dose escalation part. The sponsor will periodically review evolving aggregate safety data by appropriate methods.

CCI

